5.1.2 Subject Inclusion Criteria

Subjects must meet all the following inclusion criteria in order to be eligible for participation in this trial:

1. Willing and able to provide written informed consent/assent for the trial.
2. Male or female ≥ 18 years of age on the day of informed consent signing.
3. Histologically confirmed locally advanced or metastatic TNBC that has relapsed on or is refractory to standard of care therapy. TNBC is defined as estrogen receptor (ER), progesterone receptor, and human epidermal growth factor receptor 2 (HER2) negative. ER and progesterone receptor negativity are defined as $<10\%$ IHC staining. HER2 test result is negative if a single test (or both tests) performed show:
 - IHC 1+ or 0
 - In situ hybridization negative based on
 - o Single-probe average HER2 copy number < 4.0 signals/cell
 - o Dual-probe HER2/CEP17 ratio < 2 with an average HER2 copy number < 4.0 signals/cell

OR histologically or cytologically confirmed metastatic NSCLC that is immunotherapy naïve or previously treated with a maximum of 1 immunotherapy regimen AND chemotherapy naïve or previously treated with 1 cycle of platinum-containing chemotherapy. *EGFR/ALK* mutation-negative NSCLC patients and NSCLC patients with *EGFR* or *ALK* genomic tumor aberrations that have failed FDA-approved targeted therapy for these aberrations will be eligible for enrollment in the study.
4. Measurable disease based on RECIST 1.1, a target lesion of suitable diameter (at least 1 cm) for SBRT with the exception of a primary breast tumor, and a non-target lesion (visceral metastatic lesion) at least 1 cm in diameter for abscopal effect evaluation.
5. Willing to provide biopsy tissues as required by the study.
6. Eastern Cooperative Oncology Group (ECOG) performance status of 0 or 1.
7. Adequate organ function as defined in Table 1. All screening labs should be performed within 28 days of trial treatment initiation.

Table 1 Adequate Organ Function Laboratory Values

System	Laboratory Value
Hematological	

Absolute neutrophil count (ANC)	≥1,500/μL (without granulocyte colony stimulating factor support within 14 days of assessment)
Platelets	≥100,000/μL
Hemoglobin	≥8 g/dL without transfusion or erythropoietin dependency (within 7 days of assessment)
White blood cell count (WBC)	>2,500/μL and <15,000/μL
Lymphocyte count	≥500/μL
Renal	
Serum creatinine	<2 X upper limit of normal (ULN)
Hepatic	

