Serum total bilirubin	≤1.0 X ULN (Subjects with known Gilbert's disease who have serum bilirubin level ≤3 X ULN may be enrolled)
Aspartate transaminase (AST) and Alanine transaminase (ALT)	≤2.5 X ULN with normal alkaline phosphatase (≤5 X ULN for subjects with liver metastases) OR ≤1.5 X ULN in conjunction with alkaline phosphatase >2.5 X ULN
Albumin	≥2.5 mg/dL
Coagulation	
International normalized ratio (INR) or prothrombin time (PT)	≤1.5 X ULN unless subject is receiving anticoagulant therapy as long as PT or aPTT is within therapeutic range of intended use of anticoagulants
Activated partial thromboplastin time (aPTT)	≤1.5 X ULN unless subject is receiving anticoagulant therapy as long as PT or aPTT is within therapeutic range of intended use of anticoagulants
^a CrCl should be calculated per institutional standard.	

8. Life expectancy ≥ 6 months.
9. ≥ 4 weeks since any major surgery.
10. A 2-week washout period post any prior systemic anticancer therapy, RT, targeted anticancer therapy or mAb, and/or investigational therapy is required prior to trial entry. Subject should be recovered (i.e., ≤ Grade 1 or at baseline) from AEs due to a previously administered therapy.
 - Note: Subjects with ≤ Grade 2 neuropathy are an exception to this criterion and may qualify for the study.
11. Female subjects of childbearing potential should have a negative serum pregnancy (β-human chorionic gonadotropin [β-HCG]) within 7 days prior to receiving the first dose of the trial treatment and should not be lactating.
12. Female subjects of childbearing potential (Section 5.5.2) must be willing to use an adequate method of contraception as outlined in Section 5.5.2 – Contraception, for the course of the study through 120 days after the last dose of study medication.

Note: Abstinence is acceptable if this is the usual lifestyle and preferred contraception for the subject.
13. Male subjects of childbearing potential (Section 5.5.2) must agree to use an adequate method of contraception as outlined in Section 5.5.2 – Contraception, starting with the first dose of study therapy through 120 days after the last dose of study therapy.

Note: Abstinence is acceptable if this is the usual lifestyle and preferred contraception for the subject.

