15. Known active central nervous system metastases and/or carcinomatous meningitis. Subjects with previously treated brain metastases may participate provided they are stable (without evidence of progression by imaging for at least 4 weeks prior to the first dose of trial treatment and any neurologic symptoms have returned to baseline), have no evidence of new or enlarging brain metastases, and are not using steroids for at least 7 days prior to trial treatment. This exception does not include carcinomatous meningitis, which is excluded regardless of clinical stability.
16. Active autoimmune disease that has required systemic treatment in the past 2 years (i.e., with use of disease modifying agents, corticosteroids or immunosuppressive drugs). Replacement therapy (e.g., thyroxine, insulin, or physiologic corticosteroid

- replacement therapy for adrenal or pituitary insufficiency, etc.) is not considered a form of systemic treatment.
17. History of (non-infectious) pneumonitis that required steroids or current pneumonitis.
 18. Active infection requiring systemic therapy.
 19. History or current evidence of any condition, therapy, or laboratory abnormality that might confound the results of the trial, interfere with the subject's participation for the full duration of the trial, or is not in the best interest of the subject to participate, in the opinion of the treating investigator.
 20. Known psychiatric or substance abuse disorders that would interfere with cooperation with the requirements of the trial.
 21. Pregnant or breastfeeding, expecting to conceive or father children within the projected duration of the trial, starting with the prescreening or screening visit through 120 days after the last dose of trial treatment, or is unwilling to practice an effective method of birth control. Women of childbearing potential must have a negative serum pregnancy test within 7 days prior to administration of trial treatment.
 22. Prior treatment with gene vector therapy.
 23. Prior treatment with immunomodulatory therapy or immunotherapy (TNBC cohort only)
 24. Prior treatment with an anti-PD-1, anti-PD-L1, or anti-PD-L2 agent (TNBC cohort only).
 25. Known history of HIV (HIV 1/2 antibodies).
 26. History of liver disease such as cirrhosis or known active hepatitis B (e.g., hepatitis B surface antigen reactive) or hepatitis C (e.g., hepatitis C virus RNA [qualitative] is detected).
 27. History of or current alcohol misuse/abuse within the past 12 months.

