5.2.1.2 Dose Modification

Pembrolizumab: AEs (both non-serious and serious) associated with pembrolizumab exposure may represent an immunologic etiology. These AEs may occur shortly after the first dose or several months after the last treatment dose. Pembrolizumab must be withheld for drug-related toxicities and severe or life-threatening AEs as per Table 3 below. See Section 5.4 for supportive care guidelines, including use of corticosteroids.

Table 3 Dose Modification Guidelines for Pembrolizumab-Related AEs

Toxicity	Hold Treatment For Grade	Timing for Restarting Treatment	Treatment Discontinuation
Diarrhea/Colitis	2-3	Toxicity resolves to Grade 0-1	Toxicity does not resolve within 12 weeks of last dose or inability to reduce corticosteroid to 10 mg or less of prednisone or equivalent per day within 12 weeks
	4	Permanently discontinue	Permanently discontinue
Increased AST, ALT, or Bilirubin	2	Toxicity resolves to Grade 0-1	Toxicity does not resolve within 12 weeks of last dose
	3-4	Permanently discontinue (see exception below) ^a	Permanently discontinue
Type 1 Diabetes Mellitus (T1DM; if new onset) or Hyperglycemia	T1DM or 3-4	Hold pembrolizumab for new onset T1DM or Grade 3-4 hyperglycemia associated with evidence of beta cell failure	Resume pembrolizumab when patients are clinically and metabolically stable
Hypophysitis	2-4	Toxicity resolves to Grade 0-1. Therapy with pembrolizumab can be continued while endocrine replacement therapy is instituted	Toxicity does not resolve within 12 weeks of last dose or inability to reduce corticosteroid to 10 mg or less of prednisone or equivalent per day within 12 weeks
Hyperthyroidism	3	Toxicity resolves to Grade 0-1	Toxicity does not resolve within 12 weeks of last dose or inability to reduce corticosteroid to 10 mg or less of prednisone or equivalent per day within 12 weeks
	4	Permanently discontinue	Permanently discontinue
Hypothyroidism		Therapy with pembrolizumab can be continued while thyroid replacement therapy is instituted	Therapy with pembrolizumab can be continued while thyroid replacement therapy is instituted
Infusion Reaction	2 ^b	Toxicity resolves to Grade 0-1	Permanently discontinue if toxicity develops despite adequate premedication
	3-4	Permanently discontinue	Permanently discontinue
Pneumonitis	2	Toxicity resolves to Grade 0-1	Toxicity does not resolve within 12 weeks of last dose or inability to reduce corticosteroid to 10 mg or less of prednisone or equivalent per day within 12 weeks

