	3-4	Permanently discontinue	Permanently discontinue
Renal Failure or Nephritis	2	Toxicity resolves to Grade 0-1	Toxicity does not resolve within 12 weeks of last dose or inability to reduce corticosteroid to 10 mg or less of prednisone or equivalent per day within 12 weeks
	3-4	Permanently discontinue	Permanently discontinue
All Other Drug-Related Toxicity ^c	3 or Severe	Toxicity resolves to Grade 0-1	Toxicity does not resolve within 12 weeks of last dose or inability to reduce corticosteroid to 10 mg or less of prednisone or equivalent per day within 12 weeks
	4	Permanently discontinue	Permanently discontinue

Toxicity	Hold Treatment For Grade	Timing for Restarting Treatment	Treatment Discontinuation

Note: Permanently discontinue for any severe or Grade 3 drug-related AE that recurs or any life-threatening event.
 
^a For patients with liver metastasis who begin treatment with Grade 2 AST or ALT, if AST or ALT increases by greater than or equal to 50% relative to baseline and lasts for at least 1 week then patients should be discontinued from treatment.
 
^b If symptoms resolve within one hour of stopping drug infusion, the infusion may be restarted at 50% of the original infusion rate (e.g., from 100 mL/hr to 50 mL/hr). Otherwise, dosing will be held until symptoms resolve and the subject should be premedicated for the next scheduled dose. Refer to Table 4 – Infusion Treatment Guidelines for further management details.
 
^c Patients with intolerable or persistent Grade 2 drug-related AE may hold study medication at physician discretion. Permanently discontinue study drug for persistent Grade 2 adverse reactions for which treatment with study drug has been held that do not recover to Grade 0-1 within 12 weeks of the last dose.
			

ADV/HSV-tk oncolytic virus therapy: Significant toxicity has not been observed with the administration of ADV/HSV-tk oncolytic virus therapy alone or in combination with RT or chemotherapy in previous clinical trials.^{71, 73, 75, 76} Fever may occur due to the local inflammatory and immune response to ADV-tk, which will be treated with acetaminophen as necessary. If local inflammation is extensive or infection develops, valacyclovir will be stopped and antibiotics and/or anti-inflammatory therapy will be given as appropriate.

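### Minor safety gap: in the NSCLC cohort, a resolved Grade 4 colitis, Grade 3–4 nephritis or other life-threatening immune event on an earlier PD-1/PD-L1 agent is barred only by discretion

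*Combined protocol and SAP*

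**What the plan says.** **Entry.** Inclusion criterion 3 (Section 5.1.2) admits NSCLC patients who are immunotherapy naïve or "previously treated with a maximum of 1 immunotherapy regimen". It does not ask why that regimen ended. Exclusion 24 (Section 5.1.3) reads "Prior treatment with an anti-PD-1, anti-PD-L1, or anti-PD-L2 agent (TNBC cohort only)", and exclusion 23, on immunotherapy in general, is limited in the same way. Criterion 10 requires a 2-week washout and then "Subject should be recovered (i.e., ≤ Grade 1 or at baseline) from AEs due to a previously administered therapy".

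**Exclusions by history.** Exclusion 17 bars one immune-type event even after recovery: "History of (non-infectious) pneumonitis that required steroids or current pneumonitis". Exclusion 19 is a general clause. It covers a history of any condition or therapy that might confound the results or interfere with full participation, "or is not in the best interest of the subject to participate, in the opinion of the treating investigator".

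**On study.** Table 3 (Section 5.2.1.2) permanently stops pembrolizumab for Grade 4 diarrhea/colitis and for Grade 3–4 renal failure or nephritis. Its note adds: "Permanently discontinue for any severe or Grade 3 drug-related AE that recurs or any life-threatening event". Section 5.6 separately requires discontinuation for any AE of Grade 4 or higher and for a Grade 3 or 4 immune-mediated complication.

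**The concern.** The protocol treats the same kind of event differently on the two sides of enrolment. If it occurs on study, pembrolizumab is not resumed, even after full recovery. If it occurred on an earlier drug of the same class, the objective entry rules look only at the patient's present state.

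At stake is the safety of an individual patient, who could be re-exposed to PD-1 blockade after a severe or life-threatening reaction to it. The on-study stopping rules would act only once a new event had occurred. A second cost is inconsistency, since two investigators could decide differently about the same history.

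**Working it through.** This is mainly a reading of the text. The protocol states no figure to reproduce.

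**Step 1. Test case.** Take an NSCLC patient who had Grade 4 colitis or Grade 3–4 nephritis on an earlier PD-1/PD-L1 agent, recovered to Grade 0–1, and is off steroids with ECOG 0–1. Run this patient through the criteria that could apply.

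| Criterion | What it tests | Does it bar the patient? |
|---|---|---|
| Inclusion 3 | At most one immunotherapy regimen | No |
| Inclusion 10 | Washout and current grade | No |
| Table 1, creatinine | Current value below 2 × ULN | No, if renal function has recovered |
| Exclusion 4 | Immunodeficiency; steroids or immunosuppression in the last 7 days | No |
| Exclusion 6 | Hypersensitivity to pembrolizumab or other regimen components | Not naturally |
| Exclusion 16 | Active autoimmune disease treated systemically within 2 years | Not clearly: the disease must be active, and drug-induced events are not named |
| Exclusion 17 | Pneumonitis | No |
| Exclusions 23–24 | Prior immunotherapy or PD-1/PD-L1/PD-L2 agent | No, TNBC only |
| Exclusion 19 | Investigator's opinion | Yes, if the investigator so judges |

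Only exclusion 19 remains at entry. Section 5.6 adds that the investigator or sponsor may withdraw a subject whose enrolment was inappropriate, but that is discretionary and acts after entry.

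**Step 2. The same events on study.** Grade 4 diarrhea/colitis: permanent stop in Table 3, discontinuation in Section 5.6. Grade 3–4 nephritis: the same in both. Other life-threatening immune events: permanent stop under the Table 3 note, discontinuation in Section 5.6. The two rules agree on all three.

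**Step 3. Do other sections close the gap?** Table 6 (Section 7.2.4) requires advance sponsor approval for some rechallenges, but its rechallenge item concerns re-exposure within this study. Section 7.1.1.5.2 requires a review of prior cancer treatments without asking for their toxicity. Section 7.1.1.3 captures past conditions from the previous 10 years if the investigator considers them clinically significant.

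**Step 4. Rough check of size, not an estimate.** The documents give neither the number *m* of NSCLC patients with prior PD-1/PD-L1 treatment nor the rate of these events by grade. Section 4.1.1.4.5 reports that 2.6% of subjects in two pembrolizumab studies stopped because of an AE of special interest of any type. The cohort size is 29 (Section 8.1). With *m* assumed, expected number = *m* × 0.026, and the rate needed for one expected patient = 1/*m*:

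| *m* (assumed) | *m* × 0.026 | 1/*m* |
|---|---|---|
| 5 | 0.13 | 20% |
| 10 | 0.26 | 10% |
| 15 | 0.39 | 6.7% |
| 29 (all) | 0.75 | 3.4% |

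Even with all 29 pretreated, the rate needed (3.4%) exceeds 2.6%. The check overcounts because it includes pneumonitis and lower grades and ignores selection at entry (recovery, 7 days off steroids, ECOG 0–1). It may undercount because it covers pembrolizumab monotherapy only and misses events that did not lead to discontinuation.

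**The case against.** The strongest reply is that the protocol already handles this. Subjects who meet exclusion 19 must be excluded, its wording reaches past conditions and therapies, and a previous Grade 4 immune event fits it naturally. The investigator reviews prior treatments and every criterion, and the sponsor can withdraw an inappropriate enrolment. This stands in large part: a careful investigator would probably exclude the patient. It does not make the rule objective or uniform. Exclusion 17 shows that the protocol was prepared to write out one such history explicitly.

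A second reply is that Table 3 governs pembrolizumab reactions on study and need not set the entry standard for a remote, resolved event on another drug. This also has force. The documents give no recurrence risk after recovery, so leaving the decision to individual judgement is a defensible design choice. It limits the point to an optional improvement.

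A reader might infer that any severe past immune event should bar entry. The documents do not support that. Table 3 allows a restart after Grade 3 colitis once it resolves to Grade 0–1. Section 5.6 is stricter there, but the point relies only on events where both rules agree. Severe immune hepatitis below the life-threatening level is also unclear. Table 3 stops pembrolizumab at Grade 3–4, with an exception tied to liver metastases, while exclusion 26 ("History of liver disease such as cirrhosis or known active hepatitis B") may already cover that history.

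**Conclusion.** The gap is real but minor. For three kinds of resolved event on an earlier PD-1/PD-L1 agent (Grade 4 diarrhea/colitis, Grade 3–4 nephritis, other life-threatening immune-related events), the NSCLC entry rules rely on discretion where the on-study rules are fixed. This rests on reading exclusion 16 as not covering a recovered drug-induced event, and on treating an earlier PD-1/PD-L1 agent as comparable to pembrolizumab for this purpose.

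The number of patients cannot be estimated from the documents; well under one of 29 is a judgement that the rough check supports. It would be wrong to infer that such patients enter without any safeguard, or that the trial's results are at risk. Discretionary protection exists, and the response endpoint, sample size and analyses are unaffected. The TNBC cohort is not concerned, because prior immunotherapy is excluded there.

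**What to change.** Add to Section 5.1.3, for the NSCLC cohort only:

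> Prior Grade 4 diarrhea/colitis, Grade 3–4 immune-related renal failure or nephritis, or any other life-threatening (Grade 4) immune-related AE on an anti-PD-1/PD-L1 agent, except endocrine events controlled on replacement therapy.

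Record the worst grade of earlier immune-related AEs at the prior-treatment review under Section 7.1.1.5.2, so that the criterion can be checked.

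The line should name the events and not refer to every permanent-stop entry in Table 3. Such a reference would also take in infusion reactions, recurrent Grade 3 events, persistent Grade 2 events and Grade 3 hepatitis, which this point does not justify.

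The cost is one exclusion line by amendment and one case report form field. The downside is that an occasional pretreated NSCLC candidate becomes ineligible.

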5.1.3 Subject Exclusion Criteria

Subjects meeting any of the following exclusion criteria must be excluded from participating in the trial:

1. Unwilling or unable to comply with the study protocol.
2. Subjects for who bone metastases are the only available non-target lesions for abscopal effect evaluation.
3. Subjects with tumors for which SBRT is not considered appropriate standard therapy with the exception of subjects with a primary breast tumor. This includes subjects with target lesions less than 1 cm in diameter and those with large central lung lesions.
4. Diagnosis of immunodeficiency or is receiving systemic steroid therapy or any other form of immunosuppressive therapy within 7 days prior to the first dose of trial treatment.
5. Known history of active tuberculosis (Bacillus Tuberculosis).
6. Known or suspected hypersensitivity to pembrolizumab or any of its excipients or any component of the proposed regimen (gene vector/valacyclovir).
7. Known gallbladder or bile duct disease (i.e., infection or cholecystitis) or acute or chronic pancreatitis.
8. ECOG performance status of ≥ 2 or oxygen dependence (e.g., advanced chronic obstructive pulmonary disease).
9. Inability to swallow food or any condition of the upper gastrointestinal tract that precludes administration of oral medications (valacyclovir).
10. Congestive heart failure: New York Association class III or IV heart failure or unstable angina (see Section 12.4).
11. Sustained or clinically significant cardiac arrhythmias including sustained ventricular tachycardia, ventricular fibrillation, clinically significant bradycardia, advanced heart block (Mobitz II or higher atrioventricular nodal block), prolonged corrected QT interval (longer than 470 milliseconds), or history of acute myocardial infarction.
12. Concomitant disease(s) that could prolong QT such as autonomic neuropathy (caused by diabetes or Parkinson's disease), human immunodeficiency virus (HIV), cirrhosis, uncontrolled hypothyroidism, or cardiac failure.
13. History of syncope or family history of idiopathic sudden death.
14. Known additional malignancy that is progressing or requires active treatment. Exceptions include basal cell carcinoma of the skin or squamous cell carcinoma of the skin that has undergone potentially curative therapy or in situ cervical cancer.
15. Known active central nervous system metastases and/or carcinomatous meningitis. Subjects with previously treated brain metastases may participate provided they are stable (without evidence of progression by imaging for at least 4 weeks prior to the first dose of trial treatment and any neurologic symptoms have returned to baseline), have no evidence of new or enlarging brain metastases, and are not using steroids for at least 7 days prior to trial treatment. This exception does not include carcinomatous meningitis, which is excluded regardless of clinical stability.
16. Active autoimmune disease that has required systemic treatment in the past 2 years (i.e., with use of disease modifying agents, corticosteroids or immunosuppressive drugs). Replacement therapy (e.g., thyroxine, insulin, or physiologic corticosteroid

- replacement therapy for adrenal or pituitary insufficiency, etc.) is not considered a form of systemic treatment.
17. History of (non-infectious) pneumonitis that required steroids or current pneumonitis.
 18. Active infection requiring systemic therapy.
 19. History or current evidence of any condition, therapy, or laboratory abnormality that might confound the results of the trial, interfere with the subject's participation for the full duration of the trial, or is not in the best interest of the subject to participate, in the opinion of the treating investigator.
 20. Known psychiatric or substance abuse disorders that would interfere with cooperation with the requirements of the trial.
 21. Pregnant or breastfeeding, expecting to conceive or father children within the projected duration of the trial, starting with the prescreening or screening visit through 120 days after the last dose of trial treatment, or is unwilling to practice an effective method of birth control. Women of childbearing potential must have a negative serum pregnancy test within 7 days prior to administration of trial treatment.
 22. Prior treatment with gene vector therapy.
 23. Prior treatment with immunomodulatory therapy or immunotherapy (TNBC cohort only)
 24. Prior treatment with an anti-PD-1, anti-PD-L1, or anti-PD-L2 agent (TNBC cohort only).
 25. Known history of HIV (HIV 1/2 antibodies).
 26. History of liver disease such as cirrhosis or known active hepatitis B (e.g., hepatitis B surface antigen reactive) or hepatitis C (e.g., hepatitis C virus RNA [qualitative] is detected).
 27. History of or current alcohol misuse/abuse within the past 12 months.
 28. Major surgery within 4 weeks prior to study enrollment.
 29. Received a live vaccine within 30 days of planned start of trial therapy.
Note: Seasonal influenza vaccines for injection are generally inactivated flu vaccines and are allowed; however, intranasal influenza vaccines (e.g., Flu-Mist®) are live attenuated vaccines and are not allowed.

